5.2.8.2. PLD: Infusion-Related Reactions (Hypersensitivity Reactions)

Serious and sometimes life-threatening infusion-related reactions characterized by one of more of the following symptoms can occur with PLD: flushing, shortness of breath, facial swelling, headache, chills, chest pain, back pain, tightness in the chest and throat, fever, tachycardia, pruritus, rash, cyanosis, syncope, bronchospasm, asthma, apnea, and hypotension. The majority of the infusion-related events occur during the first infusion.

Ensure that medications to treat infusion-related reactions and cardiopulmonary resuscitative equipment are available for immediate use prior to initiation of PLD. Initiate PLD infusion at a rate of 1 mg/min and increase rate as tolerated. In the event of an infusion-related reaction, temporarily stop the drug until resolution, then resume at a reduced infusion rate. Discontinue PLD infusion for serious or life-threatening infusion-related reactions.

In order to mitigate PLD infusion-related reactions, a premedication regimen as described in [Section 5.2.3.1](#) may be administered.

PLD treatment modifications for infusion-related reactions are presented in Table 8.

Table 8. PLD Single Agent and PLD-avelumab Combination: Treatment Modification for PLD Infusion-Related Reactions

NCI-CTCAE Grade	Treatment Modification for PLD (both PLD single agent and PLD-avelumab combination*)
Grade 1 – mild Mild transient reaction; infusion interruption not indicated; intervention not indicated.	Temporarily stop PLD until resolution then resume at a reduced infusion rate per local practice.**
Grade 2 – moderate Therapy or infusion interruption indicated but responds promptly to symptomatic treatment (eg, antihistamines, NSAIDs, narcotics, i.v. fluids); prophylactic medications indicated for ≤24 hours.	Temporarily stop PLD until resolution then resume at a reduced infusion rate per local practice.**
Grade 3 or Grade 4 – severe or life-threatening Grade 3: Prolonged (eg, not rapidly responsive to symptomatic medication and/or brief interruption of infusion); recurrence of symptoms following initial improvement; hospitalization indicated for clinical sequelae. Grade 4: Life-threatening consequences; urgent intervention indicated.	Permanently discontinue PLD infusion.**
* If PLD is delayed by 1 week, avelumab should be delayed by 1 week so that PLD and avelumab are administered together. ** Following Grade 1 or Grade 2 infusion reaction to PLD, PLD should be administered as follows: 5% of the total dose should be infused slowly over the first 15 minutes. If tolerated without reaction, the infusion rate may then be doubled for the next 15 minutes. If tolerated, the infusion rate may then be completed over the next hour for a total infusion time of 90 minutes.	

5.2.8.3. PLD: Palmar-Plantar Erythrodysesthesia (Hand Foot Syndrome)

Table 9. PLD Single Agent and Avelumab-PLD Combination: Treatment modification for Palmar-Plantar Erythrodysesthesia (Hand-Foot Syndrome) (HFS)

NCI CTCAE Grade	PLD single agent	PLD-avelumab combination*
Grade 1: Mild erythema, swelling, or desquamation not interfering with daily activities.	If no previous Grade 3 or 4 HFS: Continue PLD as planned. If previous Grade 3 or 4 HFS: delay PLD dose up to 2 weeks, then resume PLD at decrease dose level.	If no previous Grade 3 or 4 HFS: Continue PLD as planned. If previous Grade 3 or 4 HFS: delay PLD dose up to 2 weeks, then resume PLD at decrease dose level. Continue avelumab as per schedule.**
Grade 2: Erythema, desquamation, or swelling interfering with, but not precluding normal physical activities; small blisters or ulcerations less than 2 cm in diameter.	Delay PLD dosing up to 2 weeks or until resolved to Grade ≤ 1 . 
 If no resolution to Grade ≤ 1 within 2 weeks, discontinue PLD. If resolved to Grade ≤ 1 within 2 weeks, and no previous Grade 3 or 4 HFS: continue PLD treatment at previous dose. If resolved to Grade ≤ 1 within 2 weeks but previous Grade 3 or 4 HFS: resume PLD treatment at decreased dose level. 	Delay PLD dosing up to 2 weeks or until resolved to Grade ≤ 1 . 
 If no resolution to Grade ≤ 1 within 2 weeks, discontinue PLD. If resolved to Grade ≤ 1 within 2 weeks, and no previous Grade 3 or 4 HFS: continue PLD treatment at previous dose. If resolved to Grade ≤ 1 within 2 weeks but previous Grade 3 or 4 HFS: resume PLD treatment at decreased dose level. Delay avelumab until resolved to Grade ≤ 1 then resume avelumab. If Grade 2 event HFS recurs, delay avelumab until resolved to Grade ≤ 1 ; then and resume avelumab.
Grade 3: Blistering, ulceration, or swelling interfering with walking or normal daily activities; cannot wear regular clothing.	Delay PLD dosing up to 2 weeks or until resolved to Grade ≤ 1 , then resume PLD treatment at decreased dose level. Discontinue PLD if there is no resolution after 2 weeks.	Delay PLD dosing up to 2 weeks or until resolved to Grade ≤ 1 , then resume PLD treatment at decreased dose level. Discontinue PLD if there is no resolution after 2 weeks. Delay avelumab until resolved to Grade ≤ 1 ; then resume avelumab. If PLD treatment was permanently discontinued and Grade ≥ 3 HFS subsequently recurs, avelumab should also be permanently discontinued.
Grade 4: Diffuse or local process causing infectious complications, or a bed ridden state or hospitalization.	Delay PLD dosing up to 2 weeks or until resolved to Grade ≤ 1 , then resume PLD treatment at decreased dose level. Discontinue PLD if there is no resolution after 2 weeks.	Delay avelumab until resolved to Grade ≤ 1 ; then resume avelumab. If PLD treatment was permanently discontinued and Grade 4 HFS recur, avelumab should also be permanently discontinued.

* For PLD-avelumab combination, PLD dosing should be managed as per PLD guidance.

**If PLD is delayed by 1 week, avelumab should be delayed by 1 week so that PLD and avelumab are administered together.

5.2.8.4. PLD: Stomatitis

Table 10. PLD Single and Avelumab-PLD Combination: Treatment Modification for Stomatitis

NCI CTCAE Grade	PLD single agent	Avelumab-PLD combination*
Grade 1: Painless ulcers, erythema, or mild soreness.	If no previous Grade 3 or 4 stomatitis: continue PLD as planned. If previous Grade 3 or 4 stomatitis: delay PLD up to 2 weeks then resume PLD at decreased dose level.	Continue avelumab as per schedule.**
Grade 2: Painful erythema, edema, or ulcers, but can eat.	Delay PLD dosing up to 2 weeks or until resolved to Grade ≤ 1 . 
 • If no resolution within 2 weeks discontinue PLD. • If resolved to Grade ≤ 1 within 2 weeks, and no previous Grade 3 or 4 stomatitis: resume PLD treatment at previous dose level. • If resolved to Grade ≤ 1 within 2 weeks, but previous Grade 3 or 4 stomatitis, resume PLD treatment at decreased dose level. 	Delay avelumab until resolved to Grade ≤ 1 , then resume avelumab. If Grade 2 stomatitis recurs delay avelumab until resolved to Grade ≤ 1 ; then resume avelumab.
Grade 3: Painful erythema, edema, or ulcers, and cannot eat	Delay PLD dosing up to 2 weeks or until resolved to Grade ≤ 1 ; then resume PLD at decreased dose level. If after 2 weeks there is no resolution, discontinue PLD.	Delay avelumab until resolved to Grade ≤ 1 then resume avelumab. If PLD treatment was permanently discontinued and Grade 3 stomatitis recurs, avelumab should also be permanently discontinued.
Grade 4: Requires parenteral or enteral support	Delay PLD dosing up to 2 weeks or until resolved to Grade ≤ 1 then resume treatment at decreased dose level. If after 2 weeks there is no resolution, discontinue PLD.	Delay avelumab until resolved to Grade ≤ 1 ; then resume avelumab. If PLD treatment was permanently discontinued and Grade 4 stomatitis recurs, avelumab should also be permanently discontinued.

* For PLD-avelumab combination, PLD dosing should be managed as per PLD guidance.

**If in the combination arm, PLD is delayed by 1 week, avelumab should be delayed by 1 week so that PLD and avelumab are administered together.

5.2.8.5. PLD: Other Non-Hematologic Toxicities and Laboratory Abnormalities

Table 11. PLD: Treatment Modification for Other Non-Hematologic Toxicities and Laboratory Abnormalities

Other non-hematologic toxicities and laboratory abnormalities	PLD
Grade 1	No PLD dose reduction
Grade 2	No PLD dose reduction
Grade 3	Delay PLD until toxicity resolves to Grade \leq 1; then resume PLD at decreased dose level
Grade 4	Delay PLD until toxicity resolves to Grade \leq 1; then resume PLD at decreased dose level

[figure not shown]
5.2.9. Left Ventricular Ejection Fraction Decreased

If a patient's LVEF drops below institutional limit of normal or by at least 15% (absolute percentage points) from baseline value, study treatment (avelumab, PLD or combination) should be discontinued. LVEF should be re-assessed within 45 days and every three months until full recovery. Upon full recovery, defined as LVEF increase to within 5% (absolute percentage points) of baseline within \leq 45 days from LVEF nadir, study treatment (avelumab, PLD or combination) can be resumed at investigator's discretion. Continuation of treatment should be followed by additional LVEF evaluation within 2 weeks.

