3.1.2. Study Treatment

Avelumab (Arm A, Arm B) 10 mg/kg will be given as a 1-hour intravenous infusion (IV) every 2 weeks (Q2W) in 4-week cycles.

PLD (Arm B, Arm C) 40 mg/m² will be given as a 1-hour IV infusion every 4 weeks (Q4W) in 4-week cycles.

In Arm B, on the days that the patient receives both infusions, PLD should be administered prior to avelumab. See [Section 5.2.3.3](#).

In all patients, study treatment may continue until PD as assessed by the investigator, unacceptable toxicity, patient refusal, patient loss to follow up, or termination of the study by the Sponsor, whichever comes first (see [Section 6.5 Patient Withdrawal](#)). Avelumab and PLD will not be continued beyond initial disease progression. For those patients who are on single-agent avelumab post-progression at the time of amendment approval, if they present with a subsequent scan showing disease progression, they must discontinue avelumab. See [Section 5.2.4](#).

For administration information, see [Section 5.2.3](#). Patients should be monitored closely for toxicity and infusion related reactions. For the management of infusion-related reactions and other toxicities, see [Section 5.2.6](#).

Patients on Arm B who are discontinued from avelumab treatment for any reason, must also be discontinued from PLD (within the scope of this study, if applicable) and entered into the 90 Day Safety Follow-up Period.

Patients on Arm B who discontinue PLD for reasons other than disease progression may continue taking avelumab until withdrawal criteria are met.

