8. Ongoing cardiac dysrhythmias of NCI CTCAE Grade ≥ 3 , atrial fibrillation of any grade, or QTcF interval >470 msec at screening (average of triplicate ECG).
9. Left ventricular ejection fraction (LVEF) <50% by MUGA or echocardiography.
10. Prior anthracycline-related cardiotoxicity or prior anthracycline exposure approaching the lifetime limit.
11. Prior organ transplantation including allogeneic stem-cell transplantation.
12. Known history of a positive test for human immunodeficiency virus (HIV) or acquired immunodeficiency syndrome (AIDS) related illness.

13. Active infection requiring systemic therapy.
14. Hepatitis B virus (HBV) or hepatitis C virus (HCV) infection at screening (positive HBV surface antigen or HCV RNA if anti-HCV antibody screening test positive).
15. Administration of a live vaccine within 30 days prior to study entry.
16. Current or prior use of immunosuppressive medication within 7 days prior to randomization. The following are exceptions to this exclusion criterion:
 - a. Intranasal, inhaled, topical steroids, or local steroid injections (eg, intra-articular injection);
 - b. Systemic corticosteroids at physiologic doses not to exceed 10 mg/day of prednisone or equivalent;
 - c. Steroids as premedication for hypersensitivity reactions (eg, CT scan premedication).
17. Active autoimmune disease that might deteriorate when receiving an immunostimulatory agents. Patients with diabetes type I, vitiligo, psoriasis, hypo- or hyperthyroid disease not requiring immunosuppressive treatment are eligible.
18. Known severe hypersensitivity reactions to monoclonal antibodies or liposomal preparations. Known hypersensitivity to any component of the Investigational Products.
19. Persisting Grade ≥ 2 toxicity related to prior therapy; however, Grade 2 sensory neuropathy or alopecia is acceptable.
20. Severe gastrointestinal conditions such as clinical or radiological evidence of bowel obstruction within 4 weeks prior to study entry, uncontrolled diarrhea in the last 4 weeks prior to enrollment, or history of inflammatory bowel disease.

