5.2.6. Recommended Dose Modifications

Every effort should be made to administer study treatment on the planned dose and schedule.

In the event of significant toxicity, dosing may be delayed and/or dose reduced as described below. In the event of multiple toxicities, dose modification should be based on the worst toxicity observed. Patients are to be instructed to notify Investigators at the first occurrence of any adverse symptom. In addition to dose modifications, investigators are encouraged to employ best supportive care according to local institutional clinical practices and according to the guidance for selected adverse events provided below.

If a PLD dose reduction is necessary, the PLD dose should be reduced initially to 30 mg/m², and then down to 20 mg/m² if a second dose reduction is required. Management of patients requiring more than 2 PLD dose reductions should be discussed with the Sponsor. Do not increase PLD dose after a prior dose reduction due to toxicity.

Table 4. Dose Modifications for PLD

Dose Level	PLD
Starting dose	40 mg/m ²
First dose reduction	30 mg/m ²
Second dose reduction	20 mg/m ²

For avelumab, no dose modifications are permitted in this study, but doses may be omitted based on persisting toxicity.

For patients on avelumab plus PLD combination treatment, PLD dose modifications as well as infusion omissions/ delays for PLD and/or avelumab may occur independently for the two drugs according to the guidance provided below for each individual drug and investigator’s medical judgment and will be reported in the CRF. If PLD is delayed by 1 week, avelumab should also be delayed by 1 week so that PLD and avelumab are administered together.

Some potential immune-related adverse events described with anti-PD-L1 drugs such as avelumab may overlap with PLD toxicities such as rash or diarrhea. For patients on avelumab or combination treatment with avelumab and PLD, any adverse event suspected to be immune-related should be managed according to the guidance for management of immune-related adverse events [Appendix 9: Management of Immune-related Adverse Events](#)). In case of a potential irAE, besides the management related to avelumab therapy, PLD doses may also be modified or interrupted based on the guidance provided for PLD toxicity management ([Section 5.2.8.2 PLD Infusion-related Reaction](#)), product labeling, and institutional guidelines according to investigator’s medical judgment.

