Additional guidance for the management of avelumab-PLD combination is provided for Neutropenia and Thrombocytopenia ([Table 7](#)), Palmar-Plantar Erythrodysesthesia (Hand-Foot Syndrome) ([Table 9](#)), and Stomatitis ([Table 10](#)).

For toxicity management, the following tables/appendix should be referenced as appropriate.

Section 5.2.7.1	Avelumab: Adverse Drug Reactions Requiring Avelumab Discontinuation or Delays
Section 5.2.7.2.1	Avelumab: Special Precautions for Administration
Section 5.2.7.2 Table 5	Avelumab: Infusion Related Reactions
Section 5.2.7.2.2	Avelumab Severe Hypersensitivity Reactions and Flu like Symptoms
Appendix 9	Avelumab: Immune related Adverse Events
Table 7	PLD and avelumab PLD combination: Treatment Modification for Neutropenia and Thrombocytopenia
Section 5.2.8.2 Table 8	PLD: Infusion-Related Reactions (Hypersensitivity Reactions)
Table 9	PLD and avelumab PLD combination: Treatment modification for Palmar Plantar Erythrodysesthesia Hand Foot Syndrome, HFS)
Table 10	PLD and avelumab PLD combination: Treatment modification for Stomatitis

Table 11	PLD: Treatment Modification for other Non-Hematologic Toxicities and Laboratory Abnormalities
Section 5.2.9	All patients: Treatment modification for Left Ventricular Ejection Fraction Decreased
Figure 2	Tumor Lysis Syndrome

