- Study Treatment:** See [5.2.3 Administration](#) for further information. Arm A: Avelumab will be given as a 1-hour intravenous infusion every 2 weeks. In the PLD + avelumab arm (Arm B), PLD will be administered on Day 1 of each cycle and on that day it will be administered first before the avelumab infusion. Also in Arm B avelumab will be given on Day 15 of each cycle. Weight should be collected prior to each infusion, assessed and documented in the CRF. There is a plus or minus 3 day window for PLD and avelumab administration but for avelumab there should not be less than 10 days between doses.
- Premedications:** For additional information about premedications for PLD and avelumab, see [Section 5.2.3.1](#) and [5.2.3.3](#). These data will not be captured in OC-RDC unless they meet the criteria for an adverse event and/or dosing toxicity, in which case, the data will be captured as an adverse event in OC-RDC.
- Tumor Assessments:** Tumor assessments will be performed according to the local standard of care and when progression is suspected, however the tumor assessment data will no longer be entered into OC-RDC. The tumor assessment scans should continue to be submitted to Parexel for storage purposes only there will be no additional BICR review.
- Adverse Event (AE) Assessments:** Adverse events should be documented and recorded in the CRF. The National Cancer Institute Common Terminology Criteria for Adverse Events (NCI CTCAE) version (v) 4.03 will be used. ([Appendix 5](#)) See [Section 8.2 Reporting Period](#) for Reporting Period details.

10. **Blood Chemistry/Hematology:** Required tests are listed in [Table 12](#). The results should be available for review prior to infusion of study treatment. These data will not be captured in OC-RDC unless they meet the criteria for an adverse event.

CC

12. **ECG:** Refer to [Section 7.1.5 Electrocardiogram Measurements](#) for additional information.
13. **LVEF: MUGA/ECHO:** Refer to [Section 5.2.9](#) for additional information.
14. **PRO questionnaires/PK/PD/ADA/Banked Biospecimen Sampling/De Novo Tumor Sample:** These assessments will no longer be performed/collected.

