6.6.8. MUGA/ECHO

LVEF% will be summarized using simple descriptive statistics (mean, SD, median, Q1, Q3, minimum, and maximum) of actual values and changes from baseline for each nominal visit over time. In addition, LVEF% will be summarized as frequency (number and percentage) of patients with:

- a shift from baseline normal to at least one result below the institutional lower limit of normal (LLN) during the on-treatment period
- \geq 10-point decrease from baseline in LVEF% during the on-treatment period
- \geq 10-point decrease from baseline in LVEF% to a post-baseline value $<$ LLN during the on-treatment period
- \geq 15-point decrease from baseline in LVEF%
- \geq 15-point decrease from baseline in LVEF% to a post-baseline value $<$ LLN during the on-treatment period.

Clinically significant findings will be listed.

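### Section 5.2.9 permits restart while LVEF is still below the limit of normal that required stopping, for patients whose baseline was less than 5 points above that limit

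*Protocol*

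**What the plan says.** Protocol Section 5.2.9 has two stop conditions. Treatment stops if LVEF "drops below institutional limit of normal or by at least 15% (absolute percentage points) from baseline value". LVEF is then re-assessed within 45 days and every three months.

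The restart test has one condition. It reads "Upon full recovery, defined as LVEF increase to within 5% (absolute percentage points) of baseline within" 45 days of the nadir. Once it is met, treatment can be resumed at the investigator's discretion, with another LVEF evaluation within 2 weeks.

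Four other places bear on this:

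- Section 5.2.6 lists the rule as "All patients: Treatment modification for Left Ventricular Ejection Fraction Decreased", so it is not confined to the PLD arms.
- Exclusion criterion 9 in Section 4.2 bars "Left ventricular ejection fraction (LVEF) <50% by MUGA or echocardiography", so the lowest baseline at entry is 50%.
- Appendix 7, the schedule in force after Amendment 2, makes LVEF assessment optional, as clinically necessary. Its footnote 13 still sends the reader to Section 5.2.9.
- SAP Section 6.6.8 tabulates "a shift from baseline normal to at least one result below the institutional lower limit of normal (LLN) during the on-treatment period". It treats the event as a move from normal to below normal.

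**The concern.** A restart criterion should at least undo the condition that caused the stop. Here the stop rule has a relative and an absolute condition, and the restart rule has only a relative one. A patient stopped for being below the limit of normal can therefore be declared fully recovered while still below it.

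The rule then gives no clear answer at the 2-week recheck. If LVEF is unchanged and below the limit, the site must either stop again after further dosing, or decide that an unchanged value has not dropped. The text does not say which.

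With a limit of 50%, the permitted restart values also lie below the minimum the protocol set for entry. The haematological rules in Section 5.2.8.1 work differently: treatment resumes only at stated absolute counts (ANC 1.5 and platelets 75 × 10⁹/L).

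What is at stake is patient safety at re-exposure, not the efficacy analysis.

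**Working it through.** The plan gives no figure to reproduce, so this is a check of the rule's logic.

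**Inputs.** B is baseline LVEF, at least 50 (Section 4.2, criterion 9). L is the institutional limit of normal, which the documents do not give, so it is varied below. v is LVEF at the recheck.

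- Stop (Section 5.2.9): v < L, or B − v ≥ 15.
- Full recovery (Section 5.2.9): v ≥ B − 5, within 45 days of the nadir.

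**Relative condition.** Recovery means B − v ≤ 5, which is less than 15. It is always cleared, with 10 points to spare.

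**Absolute condition.** Recovery and v < L hold together when B − 5 ≤ v < L. Such a v exists only if B < L + 5. Since a patient must start at or above L in order to drop below it, the affected baselines are L ≤ B < L + 5.

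**Whole-number count.** For L = 50:

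- B = 50: v = 45 to 49 (5 values)
- B = 51: v = 46 to 49 (4)
- B = 52: v = 47 to 49 (3)
- B = 53: v = 48 to 49 (2)
- B = 54: v = 49 (1)
- B = 55 or more: none

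The total is 5 + 4 + 3 + 2 + 1 = 15 combinations of baseline and recheck value. If within 5 is read as strictly less than 5, the lowest value in each row drops out and 4 + 3 + 2 + 1 = 10 remain.

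| Assumed limit L | Baselines affected | Restart allowed although below L | Combinations | If strictly less than 5 |
|---|---|---|---|---|
| 45% or lower | none | none | 0 | 0 |
| 46% | 50 | 45 | 1 | 0 |
| 48% | 50–52 | 45–47 | 3 + 2 + 1 = 6 | 2 + 1 = 3 |
| 50% | 50–54 | 45–49 | 15 | 10 |
| 53% | 53–57 | 48–52 | 15 | 10 |
| 55% | 55–59 | 50–54 | 15 | 10 |

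The baselines and values shown are for the inclusive reading.

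**Example that does not rest on the boundary.** L = 50 (assumed), B = 52, nadir 44. The fall is 52 − 44 = 8 points, so only the absolute condition stops treatment. The recheck within 45 days is 48. Since 52 − 48 = 4, this is full recovery on either reading, yet 48 < 50.

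**With the fix.** Adding v ≥ L for patients with B ≥ L leaves no value that is both recovered and below L.

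**The case against.** The best defence is that the rule does not work alone. Restart is optional, and an investigator would have to choose it below the site's own limit. LVEF is rechecked within 2 weeks. Section 5.2.8 points PLD dosing to product labelling and institutional guidelines. Appendix 9 requires avelumab to be withheld, with a cardiology consult, when imaging suggests myocarditis. Section 5.2.7.1 ends avelumab for a Grade 2 drug reaction that has not settled to Grade 1 by the following scheduled infusion, which could bar a late restart. Enrolment and the final analysis are complete, and LVEF is now measured only when a clinician sees a need.

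Most of this stands as a reason why a poor restart is unlikely. None of it supplies the missing condition. Discretion applies after the criterion is met, and the recheck comes after dosing. Neither Section 5.2.8 nor Appendix 9 gives an LVEF value for restart. Whether Section 5.2.7.1 applies depends on a causality judgement and on CTCAE grades that the protocol does not reproduce.

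A reader might infer that patients still on the combination can be re-exposed to PLD, which Section 1.2.2.5 says can damage the myocardium, while below the limit. The documents do not settle that. Section 3.1.2 says "Patients on Arm B who are discontinued from avelumab treatment for any reason, must also be discontinued from PLD" and moves them into the 90-day safety follow-up, which would close off restart in Arm B. Section 5.2.9 expressly lets the combination resume. Nothing says which prevails, so the point should not rest on PLD harm in the remaining patients.

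**Conclusion.** The gap is real and narrow. On its own terms Section 5.2.9 permits restart while its absolute stop condition still holds, and no other part of the protocol or SAP adds a limit-of-normal requirement. It affects patients whose baseline is at or above the institutional limit and less than 5 points above it. For any limit of 50% or higher, between 1 and 5 whole-number recheck values are open to each such patient. The gap survives the strict reading of within 5, for baselines up to 3 points above the limit.

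The size depends on an assumed limit, and at 45% or lower the gap disappears. How many patients have such baselines is unknown, and after Amendment 2 only those still on treatment could be affected.

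Two stronger conclusions might be drawn, and neither is supported. One is that restart is unsafe in general: for baselines 5 or more points above the limit, recovery already puts LVEF at or above it. The other is that the trial's results are compromised: no endpoint, analysis or error rate depends on this rule, and the documents do not show that anyone was restarted below the limit. This is a wording correction to a safety rule, worth making but not a major defect.

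**What to change.** Amend the definition of recovery in Section 5.2.9 along these lines:

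> Full recovery is LVEF within 5 percentage points of baseline and, where baseline was at or above the institutional limit of normal, also at or above that limit, reached within 45 days of the nadir.

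This needs no new visit, test, data field or analysis. Its cost falls on patients with a baseline 0 to 4 points above the limit, who lose the restart option at 1 to 5 whole-number values. For a baseline equal to the limit, the 5-point tolerance disappears altogether.

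An optional clarification is to say that treatment is withheld, not discontinued, pending recovery. That would remove the conflict with Section 3.1.2 for Arm B, and it fits Section 5.2.6: "For avelumab, no dose modifications are permitted in this study, but doses may be omitted based on persisting toxicity".

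A separate stop value for patients whose baseline was already below their site's limit is a different clinical decision. It is not needed to close this gap and is not proposed here. Any later protocol that reuses this paragraph should carry the added clause.
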